## **9.6 Early Termination/Discontinuation Visit**

Subjects may withdraw voluntarily from participation in the study at any time. Subjects may also withdraw voluntarily from receiving the study product Prestige LP™ Cervical Disc for any reason.

Prior to completion of the surgical treatment, an investigator may decide to forego the study treatment based on his or her medical judgment. Examples of why the surgery may not be completed as intended include but are not limited to: adverse events (AEs) or complications that occur during surgery, technical difficulties during the surgery, and anatomical findings that prevent implantation of the device(s). The reason for the termination of the study treatment by the investigator should be recorded on the Subject Disposition Electronic Case Report Form. In addition, if the termination of the study is a result of an adverse event, the event will be recorded on an Adverse Event Electronic Case Report Form and included in a summary of discontinuations, but

---

### **Medtronic Controlled Information**

the subject will not be followed for efficacy and will not be counted in the total number of study subjects.

Follow up visits for the duration of the study period are required. If a subject is discontinued from the surgery after surgery, follow up visits will not be continued.

For a subject to be identified as discontinued, the following two conditions must be met: 1) the subject or his/her representative must notify the investigational site in writing, by telephone, or in person, and 2) no data is obtained on the subject after notification of discontinuation. The reason for the discontinuation will then be recorded on the Subject Disposition Electronic Case Report Form. Missed visits after discontinuation in the study will not constitute a protocol deviation.

Subjects who fail to return for follow up visits or who do not respond to efforts in scheduling evaluations will not be considered discontinued unless the study site has been officially notified of discontinuation.

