# Prestige LP™2 Metal Concentration Clinical Investigation Plan

MDT16060SD1701

Version 6.0, 08-JUL-2019

Page 13 of 46

Medtronic

Study Procedures and Assessments	Blood collection for metal concentration testing will be performed pre-operatively and post-operatively at 6 weeks and 12 months.
Safety Assessments	Adverse events (AE) will be evaluated during and after surgery to determine the safety associated with the subject's treatment and study procedures. This data will be reported to the FDA on an annual basis until the end of the study.
Statistical Methods	Descriptive statistics will be used to summarize data from this study. Changes in metal concentration and other scores from preoperative may be assessed by using paired t-test for normally distributed data or Wilcoxon signed rank test for not normally distributed data.

---

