## 8 Selection of Subjects

### 8.1 Study Population

A total number of 30 subjects will be enrolled in this study.

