## **8.2 Subject Enrollment**

A subject is considered enrolled in this clinical study at the time at which he/she signs the subject Informed Consent. All subjects must sign the Informed Consent prior to undergoing any evaluations or procedures that are purely research-related (defined as those that would not be done if the subject was not participating in this study) or collection of study data.

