## 9.15 Assessment of Safety

The criteria outlined in this section will be used to evaluate each subject during surgery and postoperatively to determine the safety associated with the subject's treatment. The safety of the Prestige LP™ Cervical Disc treatment and metal levels will be assessed and reported to the FDA.

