7.1.3 Analysis Datasets

7.1.3.1 Primary Analysis Dataset

Primary Analysis will be conducted for the subjects who received the treatment of the PRESTIGE LP™ investigational devices at two contiguous levels. The subjects who enrolled but did not receive any

treatments or who enrolled and received the investigational treatment but exited the study following the surgery with no postoperative follow-up will not be included in this primary analysis. The missing data will not be imputed, and the analysis will be based on the observed data. However, the data prior to the secondary failure will be carried forward to the latest visit for those who had a secondary surgery failure.

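### Protocol 9.6 and the SAP's two datasets can leave an adverse event during or soon after surgery out of the AE rates, because no safety set is defined

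*Protocol*

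**What the plan says.** **Counting.** Protocol 8.1: "A total number of 30 subjects will be enrolled in this study". Protocol 8.2: "A subject is considered enrolled in this clinical study at the time at which he/she signs the subject Informed Consent". Protocol 8.5 adds that withdrawn subjects are not replaced. SAP 6 describes the thirty as receiving the two-level treatment.

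**Surgery not completed.** Protocol 9.6 foresees this and gives as examples "adverse events (AEs) or complications that occur during surgery, technical difficulties during the surgery, and anatomical findings that prevent implantation". Where the termination results from an AE, "the event will be recorded on an Adverse Event Electronic Case Report Form and included in a summary of discontinuations", but "the subject will not be followed for efficacy and will not be counted in the total number of study subjects".

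**Scope of the safety assessment.** The synopsis says "Adverse events (AE) will be evaluated during and after surgery to determine the safety associated with" the treatment. Protocol 9.15 sets criteria to "evaluate each subject during surgery and postoperatively to determine the safety". Protocol 9.15.3, however, commits to analysing AE information from after surgery onward.

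**Analysis sets.** SAP 7.1.3.1: "Primary Analysis will be conducted for the subjects who received the treatment" at two contiguous levels. Two groups are left out: enrolled subjects who received no treatment, and treated subjects who exited after surgery with no postoperative follow-up. SAP 7.1.3.2 makes the per-protocol set a subset of this one, used for overall success alone. SAP 7.8.2.8 runs life tables for all AEs, implant-associated AEs, Grade 3 or 4 AEs and their combination, without naming a set.

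**The concern.** Safety as shown by AEs is a secondary objective, and AE data go to FDA every year. An AE serious enough to stop the implantation is one that a reader of those rates would want to see. The protocol gives a rule for taking such a subject out of the study count, and the SAP has no set that puts the subject back. Someone producing the tables from the defined sets would omit both the event and the subject. That error runs in one direction: it can only make the AE rate look lower. In a study of 30, each subject is worth 1/30 = 3.3 percentage points.

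**Working it through.** The documents give no AE rate, power or precision figure to reproduce. The 30 is tied only to the FDA condition of approval (SAP 6). The check is therefore on the rules first, with arithmetic as illustration.

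**Step 1: follow four kinds of enrolled subject through the rules.**

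| Subject | Protocol 9.6 count | SAP primary set | SAP per-protocol set |
|---|---|---|---|
| Stopped by an AE, no disc placed | Not counted | Out (untreated) | Out |
| Stopped by an AE, one disc placed | Not counted | Fails the two-level condition; not named among the exclusions | Out if not in the primary set |
| Stopped for a technical or anatomical reason, no disc placed | No rule stated | Out (untreated) | Out |
| Both discs placed, exits with no follow-up | No non-count rule stated | Out | Out |

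None of the four is clearly in a defined set. SAP 7.8.2.8 names none, so whether their AEs enter the life tables is undefined. If the primary set is used by default, they do not.

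**Step 2: direction.** Let n be the enrolled subjects who reach surgery and x the number of other subjects with an AE of the type considered. Take one further subject with such an AE who is dropped.

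- Rate if dropped: x/(n − 1)
- Rate if kept: (x + 1)/n
- Kept minus dropped: (n − 1 − x) / [n(n − 1)]

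This is positive whenever x < n − 1, that is, whenever at least one remaining subject is event-free.

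**Step 3: size.** Take n = 30 (Protocol 8.1), no replacement (8.5) and no other losses. The numbers of exits and other events are assumed. Simple proportions stand in for life-table rates. Intervals are exact (Clopper-Pearson) 95%.

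| Exits | Other events | Dropped | Kept |
|---|---|---|---|
| 1 | 0 | 0/29 = 0% (0 to 11.9%) | 1/30 = 3.3% (0.1 to 17.2%) |
| 1 | 3 | 3/29 = 10.3% (2.2 to 27.4%) | 4/30 = 13.3% (3.8 to 30.7%) |
| 2 | 0 | 0/28 = 0% (0 to 12.3%) | 2/30 = 6.7% (0.8 to 22.1%) |

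If 30 instead means 30 treated, and one uncounted subject comes on top, the first row becomes 0/30 = 0% against 1/31 = 3.2%. The direction and rough size are the same under either reading.

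**Step 4: how likely is one exit?** The documents give no risk of an AE-stopped implantation. For an assumed per-subject risk p, the chance of at least one among 30 is 1 − (1 − p)^30: 26% at p = 1%, 46% at 2%, 60% at 3% and 79% at 5%.

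**The case against.** The case against has several parts, and much of it stands.

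- **The event is not lost.** A reader might infer that the AE vanishes. It does not. Protocol 9.6 puts it on the AE form and in a discontinuation summary, Table 2 and 9.3 provide for AE recording at surgery, and 11.2 makes all AEs reportable with aggregate review at least annually. What is at risk is the AE rate.
- **The SAP does not expressly exclude the event.** Its exclusions are worded for the primary analysis, while AEs are a secondary objective. A statistician could use all operated subjects without breaching 7.8.2.8. The exclusion is an inference from two sets that do not fit, together with the no-count rule. This limits the point to a rate that can be biased; it does not remove the gap.
- **Removal is not outcome-dependent throughout.** The SAP sets turn on two-level treatment whatever the reason for stopping. Only the 9.6 clause is tied to AEs, and its loose drafting (it moves from termination of the study treatment to termination of the study) means that the contrast with technical or anatomical causes may be accidental. The documents do not support reading it as a deliberate removal of bad outcomes.
- **Device exposure matters.** A subject with no disc has no implant exposure and would dilute an implant-associated rate: for example, 3/29 = 10.3% would become 3/30 = 10.0%. This stands and shapes the fix.
- **It is not settled that 30 means consented.** Protocol 8.1, 8.2 and 8.5 point to consented subjects; SAP 6 and the 9.6 clause can be read as treated subjects. The review should ask for reconciliation and not choose.
- **Size is hypothetical.** The exit counts are assumed, the paired intervals overlap heavily, and the study is descriptive. The bias nevertheless has a known direction and costs little to remove.

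**Conclusion.** The point holds in this form: as the rules stand, an intraoperative or perioperative AE can be left out of the AE rates, and any such omission lowers them. It rests on a stated non-count rule in Protocol 9.6, on two SAP datasets that both require two-level treatment, on the exclusion of implanted subjects without follow-up, and on AE life tables with no named set. The protocol's differing statements on whether AEs during surgery are in scope add to the uncertainty.

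The effect is about 3 percentage points per omitted subject in a study of 30. It is zero if no surgery is stopped by an AE and no implanted subject is lost before follow-up. The metal-concentration analyses are unaffected, and no power or precision target is involved. The change is worth making before the AE tables are produced, but the point does not threaten the primary objective.

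**What to change.** **SAP now**

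- 7.1.3: add a safety set of all subjects in whom the index surgery was started, whether or not both discs were placed or any follow-up occurred.
- 7.8.2.8: use that set for the all-AE and Grade 3 or 4 summaries, with events in subjects who did not receive both discs on a separate line. Keep the implant-associated rates on subjects who received at least one disc.
- 7.1.1: add a disposition row for surgery started but two-level treatment not completed, by reason. The existing list is open-ended but has no such line, and the SAP text does not specify the discontinuation summary that 9.6 promises.
- Leave the primary set as it is for metal concentrations and clinical outcomes.

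**Protocol, at the next amendment**

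- Reconcile the 9.6 counting clause with 8.1, 8.2, 8.5 and SAP 6, stating whether 30 means consented or treated.
- Reconcile 9.15.3 with the synopsis and 9.15 on AEs during surgery.

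**Cost.** One dataset definition, one table line and one disposition row. No new data are needed for subjects stopped at surgery, because 9.6 already requires the AE and Subject Disposition forms. The protocol wording needs sponsor approval and IRB submission under 15.11, which is why it can wait. The reported AE rate may come out slightly less favourable.

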## **9.7 Subject Consent**

This study will be conducted in full compliance with the informed consent regulations in 21 CFR 50. All subjects for this study will be provided a consent form describing this study and providing sufficient information for subjects to make an informed decision about their participation in this study. This consent form will be submitted with the protocol for review and approval by an IRB(s). The Investigator is responsible for obtaining the formal consent of a subject (competent to do so and not under duress), using the IRB-approved Informed Consent Form (ICF); and this consent will be obtained before the subject undergoes any study procedure(s). This ICF must be signed by the subject or legally acceptable representative, and the Investigator-designated study personnel obtaining the consent. A copy of the signed ICF will be given to the subject and the original retained by the investigator with the site's copy of the eCRFs.

The informed consent form must be reviewed and approved by the Sponsor and the governing IRB prior to initiation of the study at a clinical site.

## **9.8 Planned Study Closure**

Study closure is defined as closure of a clinical study that occurs when Medtronic and/or regulatory requirements have been satisfied per the Clinical Investigational Plan and/or by a decision by Medtronic or regulatory authority, whichever occurs first. Study Closure is a process initiated by distribution of an initial study closure letter. The study closure process is complete upon distribution of the Final Report or after final payments, whichever occurs last.

## **9.9 Unblinding Procedures**

This is a single arm study; therefore, no subjects will be randomized and unblinding of subjects will not be needed.

---

### **Medtronic Controlled Information**

## **9.10 Monitoring Subject Compliance**

Subject follow-up is crucial to the outcome of the clinical study. Subjects should be informed of the importance of returning for follow-up visits within the prescribed windows.

## **9.11 Measures to Minimize Bias**

This is a single arm study and all subjects will receive the same surgical treatment. Subjects enrolled in this study must meet all inclusion criteria and no exclusion criteria as stated in this protocol in Section 8.3 and 8.4 respectively. No study site will be allowed to enroll more than one third of the total enrollment.

This study will be run in compliance with 21 CFR 54 with financial disclosures being obtained from all participating Investigators, by the Sponsor at the beginning of the study and at the completion of the study. If any changes occur during the course of the study, it is the Investigator's responsibility to notify the Sponsor and provide a new financial disclosure to document the change.

## **9.12 Study Supplies**

The study Sponsor will provide each study site with any required binders for keeping of study related documents as applicable.

## **9.13 Medication Compliance**

### **9.13.1 Permitted Treatment(s)**

- Unless not medically feasible, the use of NSAIDs is recommended for two weeks postoperatively.
- The use of non-steroidal anti-inflammatory drugs such as; Toradol (ketorolac) and PO Naprosyn (naproxen) is acceptable.
- Use of a soft cervical collar is recommended as needed.

### **9.13.2 Post-Operative Prohibited Treatment(s)**

- Electrical bone growth stimulation should not be used for treatment of the cervical spine during the 12-month follow-up period.
- Current use of or previous chronic use of prescription drugs [e.g., Cloxacillin, an antibiotic used for prophylaxis against surgical infections, and/or Clotrimazole].
- 

## **9.14 Assessment of Efficacy**

Efficacy will be assessed using the secondary measurements of this study.

---

### **Medtronic Controlled Information**

## 9.14.1 Efficacy Measures

The efficacy measures will be determined by the measurements listed in the sections below.

## 9.14.2 Pain/Disability Status

The self-administered Neck Disability Index (NDI) Questionnaire (Vernon and Mior, 1991) will be used. Success for each individual subject will be defined as pain/disability improvement postoperatively according to the following definition:

Preoperative Score-Postoperative Score  $\geq 15$

Success in this category is a criterion for overall success.

## 9.14.3 Pain Status

### Neck Pain Score

Numerical rating scales adapted in part from Measuring Health (McDowell and Newell, 1996) will be used to evaluate neck pain. This method of analyzing pain is further discussed in "Clinical applications of visual analogue scales; a critical review." In this clinical trial, neck pain is described as a composite of pain intensity and duration and is derived by adding the numerical rating scores from the pain intensity and duration scales.

### Arm Pain Score

Numerical rating scales as described above will also be used to measure arm pain.

## 9.15 Assessment of Safety

The criteria outlined in this section will be used to evaluate each subject during surgery and postoperatively to determine the safety associated with the subject's treatment. The safety of the Prestige LP™ Cervical Disc treatment and metal levels will be assessed and reported to the FDA.

## 9.15.1 Safety Endpoint(s)

## 9.15.2 Neurological Status

Neurological status will be evaluated preoperatively and postoperatively. Neurological status is based on motor function, sensory function, and reflexes. Each of the categories is comprised of a

---

 Vernon, H and Mior S (1991). The Neck Disability Index: A Study of reliability and validity. *J. Manipulative Physio Ther* 1991; 14:409-415.

 McDowell, I. and Newell, C. (1996). *Measuring Health; a Guide to Rating Scales and Questionnaires* (2nd Edition). New Your: Oxford University Press.

## Medtronic Controlled Information

number of elements. The measurements will be recorded on the Neurological Status Electronic Case Report Form.

Postoperative evaluations of each element on the Neurological Status Electronic Case Report Form will be compared to the preoperative evaluations. Success will be defined as maintenance or improvement in each element for the time period evaluated.

#### **9.15.3 Adverse Events**

All reported AE information, as defined in Section 11, for a patient after surgery and throughout their participation in the study will be included in the study database and will be analyzed. This analyzed data will be reported to the FDA on an annual basis until the end of the study. AEs related to Medtronic products will be entered into the quality system, at which time further determinations on reporting requirements will be made.

The follow-up report should give full details of the experience, including an assessment of the relationship to the test article(s), and will be sent to the Sponsor promptly. SAEs will then be reported to regulatory authorities by the Sponsor.

#### **9.15.4 Device Deficiency**

A device deficiency is inadequacy of a medical device with respect to its identity, quality, durability, reliability, safety, or performance. Note: Device deficiencies include malfunctions, use errors, and inadequate labeling. If a device deficiency causes an adverse event to the subject, then an Adverse Event Electronic Case Report Form is completed. If a device deficiency does not cause an adverse event, then complete the Device Deficiency Electronic Case Report Form.

### **9.16 Clinical Laboratory Tests**

All subjects enrolled in this clinical study, who undergo surgical treatment with the Prestige LP™ Cervical Discs will be required to have their blood drawn at specified time intervals, to be analyzed for metal concentrations. Each blood serum sample will be analyzed for the concentration of titanium, vanadium and aluminum. The metal concentrations at each postoperative evaluation will be summarized using descriptive statistics and will be compared against the preoperative baseline measurements. Guidelines specific to the blood collection procedure and metal concentration testing procedure are provided as an attachment to this protocol in Appendix I.

#### **9.17 Pregnancy Reporting**

The Investigator must report all pregnancies to the Sponsor immediately after becoming aware of the event. Subjects who become pregnant during the study will be followed until the completion of pregnancy and lactation (if applicable), and outcomes will be collected on both mother and child. The pregnancy will not be considered an adverse event, unless a complication resulting from the pregnancy is reported.

---

#### **Medtronic Controlled Information**

## 9.18 Cancer Reporting

In the event that a subject experiences an AE involving a cancer diagnosis during the study, the Investigator should make every attempt to provide the pathology report (if available); histopathology; other co-morbid medical diagnoses; applicable laboratory reports (e.g., complete blood count (CBC); and the age of onset. The Investigator must report all AEs involving a cancer diagnosis to the Sponsor or Sponsor's representative immediately after becoming aware of the event.

As part of study enrollment, each subject will be asked to provide information on his/her cancer history.

## 10 Risks and Benefits

### 10.1 Potential Risks

The potential risks in this study may include but are not limited to:

- **Surgical procedure (any):** wound, local and/or systemic reactions and/or infection and/or adverse reactions to anesthesia
- **Surgical procedure (spine):** dysphagia, dysphonia, hoarseness and other tracheal, esophageal or pharyngeal conditions
- **Artificial Disc Device:** loosening, bending or breakage of the components and/or other difficulties with the position of the implant
- **X-rays:** known risks to participating in the study include subject exposure to radiation from cervical spine x-rays
- **Blood Draw:** The risks involved in taking blood include, but are not limited to: swelling, bruising, or infection around the vein where blood is collected. During and after this procedure, the subject may feel dizzy or may faint.

### 10.2 Potential Benefits

The potential benefits from this study allow the Sponsor to assess potential safety concerns related to the presence of metal concentrations in the blood of subjects who undergo surgical treatment with the Prestige LP™ Cervical Disc.

### 10.3 Risk-Benefit Rationale

Any risks associated with participation in this clinical study will be minimized and managed in accordance with and full compliance to 21 CFR 50, 56.

---

